#### C. Study Design and Research Methods

This study is an open label, cross-over study, evaluating the plasma and peritoneal fluid pharmacokinetics of dalbavancin after either intravenous or intraperitoneal administration. The

patients will be randomly assigned to receive dalbavancin either intravenously or intraperitoneally on study visit 1. The patients will receive the alternate administration technique following the washout period at visit 4. Patients will be administered dalbavancin either intravenously or intraperitoneally on study day 0. Pharmacokinetic analysis will be conducted on days 0, 7, and 14. Following the wash out period of 45 days or greater, the same 10 patients will cross-over and then be administered dalbavancin via the alternate administration technique received in visit 1 on study day 0. Pharmacokinetic analysis will be conducted again on days 0, 7, and 14. (see Appendix 1)

*Sample Size:*

Ten (n=10) patients will be evaluated in this pharmacokinetic evaluation. Since this is a descriptive pharmacokinetic study a sample size calculation was not performed

*Plasma and peritoneal fluid sampling:*

Dalbavancin will be administered on study day 0. On the intravenous administration day dalbavancin will be administered as a 30-minute IV infusion. On the intraperitoneal administration day, dalbavancin will be administered in the peritoneal dialysis fluid with a 6 hour dwell time. On day 0, patients will undergo plasma and peritoneal fluid pharmacokinetic sampling for determination of dalbavancin concentrations at time zero, 1 hour, 2 hours, 3 hours, 4 hours, 6 hours, at time of volume exchange. Patients will be given a specimen collection cup and asked to collect ~30 ml of peritoneal dialysate following scheduled nocturnal dwell approximately 24 hours following the administration of dalbavancin administration. Patients will report for a single PK measurement on study days 7 and 14. (18 total plasma and 18 total peritoneal fluid samples per patient). Blood samples will be drawn from a peripherally inserted intravenous catheter. Peritoneal fluid samples will be drawn from the already placed peritoneal dialysis catheter. Blood samples will be immediately centrifuged at 3000g and plasma and peritoneal fluid samples will be stored at -80°C until analysis.

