##### *Pharmacokinetic analysis:*

Plasma and peritoneal fluid concentration-time data for dalbavancin will be evaluated using a multi-compartment model in Phoenix WinNonlin (Pharsight corporation). One, two, and three compartment models will be explored. The following PK parameters will be calculated for plasma and dialysate samples: Cmax – measured, Tmax – measured, Cmin – measured. Fraction of intraperitoneal (IP) dose absorbed [(Dose – drug concentration remaining in dialysate at end of

antibiotic dwell)/Dose].  $K_{el}$  – elimination rate constant.  $T_{1/2} = 0.693/K_{el}$ .  $K_{pc0-6}$  – rate constant for distribution of dalbavancin from peritoneal cavity between 0-6 hours. Distribution half-life in the peritoneal cavity between 0-6 hours ( $t_{1/2} = \ln 2/k_{pc0-6}$ ). Clearance systemic =  $(F \times \text{Dose})/AUC_{0-\infty}$ . Clearance peritoneal – dalbavancin concentration in spent dialysate/AUC of peritoneal fluid. Non-dialysis clearance –  $Cl = Cl_{plasma} - Cl_{peritoneal}$ .  $AUC_{0-\infty}$  – linear trapezoidal method.  $AUC_{0-12}$  hours – linear trapezoidal method. Volume of distribution for each compartment –  $Cl/k_{el}$ ; nonsteady state equations will be utilized. The ratio of plasma dalbavancin to dialysate plasma concentration at each time point –  $C_{plasma}/C_{dialysate}$  and via  $AUC_{plasma}/AUC_{dialysate}$ . Given the sample size of 10 patients completing each treatment modality we will be able to calculate means and standard deviations for all included pharmacokinetic parameters. We will incorporate the dalbavancin PK parameters into a nonlinear mixed effects model (NONMEM) or ADAPT II to determine the pharmacokinetics and examine the effects of varying dosing strategies on plasma and peritoneal fluid concentrations.

*Analysis of pharmacodynamic targets:*

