Pharmacodynamic parameters will be evaluated in order to determine whether dalbavancin dosing results in initial and steady-state plasma and peritoneal concentrations that are adequate for treatment of infections due to common pathogens (Staph aureus, Coag neg staph, and enterococcus). Monte Carlo simulation (Crystal Ball version 7, Decisioneering, Inc., Denver, CO) will be used in this study to calculate probability of target attainment (PTA) for pharmacodynamic goals. The model randomly applies values for  $C_{max}$  and  $AUC_{0-12}$  derived from data obtained from the study patients. We will utilize CLSI and EUCAST MIC data for the common gram positive pathogens. We will place these MIC distributions into our Monte Carlo simulation for comparison to dalbavancin plasma concentrations and PK variability. From these studies, MIC frequency distributions will be constructed and used in the Monte Carlo simulations. Ten thousand simulations will be performed at each MIC value and for each of the selected pathogens.

[figure not shown]
[figure not shown]
*Statistical comparisons of PK/PD findings*

Intra-patient pharmacokinetics and pharmacodynamics of dalbavancin will be compared between intravenous and intraperitoneal administration using the paired-t test. Given the sample size of 10 patients completing each phase of the study, we will be able to detect a mean difference in area under the curve between the two treatment modalities of 1527 mg·hr/L at a power of 80%. Probability of target attainment will be compared with the paired t-test. Statistical comparisons will be compared using SAS version 9.3. A p-value < 0.05 will be considered significant.

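### The simulation of target attainment (PTA) specifies no step that carries the sampling error of its 10 patients into the result, and 10,000 draws cannot supply it

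*Combined protocol and SAP*

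**What the plan says.** All references are to the combined protocol and SAP.

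- **Sample size** (section IV.C): "Ten (n=10) patients will be evaluated in this pharmacokinetic evaluation". The section calls the study descriptive and gives no sample size calculation.
- **Summaries** (section IV.F, Pharmacokinetic analysis): "Given the sample size of 10 patients completing each treatment modality we will be able to calculate means and standard deviations". No standard error or confidence interval is named.
- **Simulation inputs** (section IV.F, Analysis of pharmacodynamic targets): Cmax and AUC0-12 values, "derived from data obtained from the study patients", are applied at random. Published MIC distributions are then entered "for comparison to dalbavancin plasma concentrations and PK variability".
- **Simulation size** (same subsection): "Ten thousand simulations will be performed at each MIC value and for each of the selected pathogens".
- **Use of the result** (same subsection): the analysis is meant to show whether plasma and peritoneal concentrations are adequate to treat infection by the common gram-positive pathogens.
- **Population model** (section IV.F, Pharmacokinetic analysis): "We will incorporate the dalbavancin PK parameters into a nonlinear mixed effects model (NONMEM) or ADAPT II". Its stated purposes are to determine the pharmacokinetics and to examine dosing strategies. It is not linked to the PTA simulation.

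The plan does not say whether the simulation resamples the 10 observed values or draws from a fitted distribution, or what shape such a distribution would have. It sets no PTA threshold for adequacy.

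**The concern.** A simulated PTA has two separate sources of error. One comes from using a finite number of draws, and 10,000 draws make it negligible. The other comes from knowing the exposure distribution only through 10 patients, and no number of draws reduces it. The plan fixes the draw count but describes nothing that would measure the second error. Followed as written, it gives PTA point estimates without any indication of their main uncertainty.

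This matters because PTA is the plan's link from measured concentrations to a judgement that they are adequate for treatment. In a fitted distribution, PTA depends on the lower tail, and so on an SD estimated with 9 degrees of freedom. If the observed values are resampled instead, PTA for one metric at one fixed MIC can move only in steps of 10 points. Either way, an adequacy statement could owe much to which 10 patients were enrolled.

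**Working it through.** **The plan's own figures.** The plan gives no precision for PTA, so there is none to reproduce. Its one power figure, a detectable AUC difference of 1527 mg·hr/L, comes without an SD and plays no part in this check.

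**Inputs.** From the plan: n = 10 patients (IV.C) and 10,000 draws (IV.F). Assumed: 10 independent completers per route, exposures normal or log-normal, a fixed target at a single MIC, and a mean and SD estimated from the sample. The single-MIC intervals below need neither the CV nor the target value, which the plan does not give.

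**Step 1: Monte Carlo error.** The 95% half-width is 1.96 × √[p(1 − p)/10,000].
- p = 0.50: 1.96 × 0.005 = 0.98 points
- p = 0.90: 1.96 × 0.003 = 0.59 points
- p = 0.95: 0.43 points

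**Step 2: sampling error of 10 patients, fitted distribution.** The reported PTA is Φ(k), where k = (sample mean − target)/sample SD on the normal or log scale. The quantity k√10 follows a noncentral t distribution with 9 df and noncentrality √10 × Φ⁻¹(true PTA). The limits are the values of true PTA for which the observed k√10 lies at the upper or lower 2.5% point.

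For a reported 90%, k = 1.2816 and k√10 = 4.053. The limiting noncentralities are 1.305 and 6.685. Dividing by √10 gives 0.413 and 2.114, so the limits are Φ(0.413) = 0.66 and Φ(2.114) = 0.98.

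| Reported PTA, single MIC | 95% interval | Width (points) |
|---|---|---|
| 50% | 27% to 73% | 46 |
| 80% | 54% to 94% | 40 |
| 90% | 66% to 98% | 32 |
| 95% | 74% to 99.5% | 25 |
| 99% | 86% to 99.98% | 14 |
| 99.9% | 94% to 100% | 6 |

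**Step 3: resampling instead.** The exact binomial (Clopper-Pearson) interval is 55% to 99.7% when 9 of 10 patients attain the target, and 69% to 100% when 10 of 10 do.

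**Step 4: the whole chain.** Studies of 10 patients, each with a fitted mean and SD and a true PTA of 90%, were simulated. With 10,000 draws per study, 95% of studies report a PTA between about 73% and 99.6%. With 1,000,000 draws the range is essentially the same (72% to 99%).

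**Step 5: chance of an optimistic result.** Suppose 90% were the cut-off for adequacy. This is an assumption, since the plan states none. If the true single-MIC PTA is 80%, the noncentrality is √10 × 0.8416 = 2.661, and P(noncentral t with 9 df ≥ 4.053) = 0.176. A PTA of 90% or more would be reported about 18% of the time.

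**Step 6: attainment averaged over MICs.** The illustration assumes five doubling dilutions weighted 5/25/40/25/5%, log-normal exposure and a true weighted attainment of 90%. The central 95% of reported values is:
- CV 20%: 85% to 94%
- CV 40%: 83% to 95%
- CV 60%: 80% to 96%

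That is roughly 10 to 16 points, against about 26 points for single-MIC PTA (73% to 99.6%, step 4). The weights and CVs are not in the plan.

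**The case against.** **Silence is not a decision.** A reader might infer that the plan treats the 10-patient estimates as exactly known, or that it will present PTA as accurate to under a point. The documents say neither. They name no uncertainty step but do not exclude one, they do not state the reporting precision, and two figures in this part of the plan were not available for review. What stands is narrower: the software, inputs and draw count are specified, and none of them yields an interval. The mixed-effects model could supply parameter uncertainty, but the plan does not connect it to PTA.

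**The error is not always tens of points.** This is correct. Fitted-distribution intervals are about 14 points wide at 99% and 6 at 99.9%. The plan describes very high potency against staphylococci, so part of the curve may lie near 100%. MIC-weighted attainment is also steadier (step 6). The large widths apply to single-MIC PTA of about 50% to 95%. Under resampling, however, even 10 of 10 leaves a lower limit of 69%.

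**Comparison of routes.** A reader might conclude that one route could be declared better on noise. The plan says "Probability of target attainment will be compared with the paired t-test" without stating the unit of analysis. If PTA values for individual patients are paired, variation among the 10 is already in the test. The documents do not support that conclusion, and it is not claimed here.

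**Descriptive study.** PTA is neither a primary nor a secondary endpoint, and this limits the weight of the point. It does not remove it, because the plan uses PTA to judge adequacy for treatment.

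**Conclusion.** The concern holds in limited form. The plan bases PTA on the exposures of 10 patients and specifies no step that carries their sampling error into the result. The 10,000 draws control an error of at most about 1 point. The error left unmeasured gives a 95% interval 25 to 40 points wide for a reported single-MIC PTA of 80% to 95%. It is smaller close to 100% and for MIC-weighted attainment. The single-MIC widths rest on normal or log-normal exposures and 10 completers, and fewer completers would widen them. The 18% figure rests on an assumed 90% cut-off, and the 10 to 16 points on assumed MIC weights and CVs. The primary pharmacokinetic results are unaffected. The adequacy statement should not be made without the interval.

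**What to change.** In section IV.F, Analysis of pharmacodynamic targets, place an outer loop of at least 1,000 repetitions around the planned simulation. Each repetition either resamples patients or draws the log-mean and log-SD from their sampling distribution. The inner loop then draws log-normal exposures and computes PTA as planned. Report every PTA, per MIC and MIC-weighted, with the 95% interval from the outer loop, and base the statement on adequacy for treatment on that interval.

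Resampling patients cannot show uncertainty when all 10 attain the target and only observed values are used, so in that case draw from the fitted distribution or give the exact binomial limit. A closed-form interval, as in step 2, is a simpler alternative for single-MIC PTA.

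The cost is a little more programming, with no new patients, samples or visits. The downside is that intervals at n = 10 will be wide and the adequacy statement less favourable.

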### **I. Hypotheses and Specific Aims:**

#### Hypothesis:

Dalbavancin maintains adequate plasma and peritoneal fluid concentrations for 2 weeks after a single 1500 mg dose when administered intravenously or intraperitoneally, making it a viable and convenient option for treating peritoneal dialysis patients with peritonitis

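### The plan compares probability of target attainment by paired t-test, but the simulation it describes gives no value per patient and route to pair.

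*Combined protocol and SAP*

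**What the plan says.** Section IV.F, under the pharmacodynamic targets, says that Monte Carlo simulation "will be used in this study to calculate probability of target attainment (PTA) for pharmacodynamic goals". The inputs are Cmax and AUC0-12 values "derived from data obtained from the study patients", applied at random and set against MIC distributions. On scale it says: "Ten thousand simulations will be performed at each MIC value and for each of the selected pathogens". Three pathogen groups are named.

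The next part of IV.F, on statistical comparisons, opens with: "Intra-patient pharmacokinetics and pharmacodynamics of dalbavancin will be compared between intravenous and intraperitoneal administration using the paired-t test". After a sentence on the detectable AUC difference with 10 patients, PTA gets a sentence of its own: "Probability of target attainment will be compared with the paired t-test". That sentence names neither the pair nor the groups compared. Significance is set at p < 0.05.

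Three places limit the weight. Section IV.A does not list PTA among the endpoints. Section IV.C says "Since this is a descriptive pharmacokinetic study a sample size calculation was not performed". The hypothesis in Section I, "Dalbavancin maintains adequate plasma and peritoneal fluid concentrations for 2 weeks after a single 1500 mg dose", is put forward for administration by either route and is not a claim about the difference between them.

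**The concern.** A paired t-test needs a unit that contributes one value under each condition, and its degrees of freedom come from the number of such units. The simulation as described yields one proportion per MIC value and pathogen, presumably for each route. The units ready to hand are therefore draws, MIC levels or MIC-by-pathogen cells. All of these are set by the analyst, and all rest on the same 10 patients' exposures, so adding more of them adds no information about patients.

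Two analysts could follow the sentence faithfully and report opposite conclusions from the same data. A reader would take the resulting p-value, judged at 0.05, as evidence about the routes of administration.

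**Working it through.** **Inputs from the documents.** 10 patients in a two-period crossover (IV.C); 10,000 simulations per MIC value and pathogen, three pathogen groups, threshold 0.05 (IV.F). The plan gives no figure for PTA to reproduce. The only power figure nearby, 1527 mg·hr/L, concerns AUC, comes without a standard deviation, and is not used here.

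**Step 1: look for the unit.** The pharmacokinetic part of IV.F derives parameters from the concentration data. Its NONMEM or ADAPT II step concerns pharmacokinetics and dosing strategies and is not linked to PTA. The simulation step gives results by MIC and pathogen. No visible step gives a PTA per patient and route.

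**Step 2: draws as pairs.** With N independent draws per route and attainment p₁ and p₂, t = (p₁ − p₂) / √{[p₁(1 − p₁) + p₂(1 − p₂)] / N}. For 0.95 and 0.94 the bracket is 0.0475 + 0.0564 = 0.1039.

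- N = 1,000: t = 0.01 / 0.01019 = 0.98, p = 0.33
- N = 5,000: t = 0.01 / 0.00456 = 2.19, p = 0.028
- N = 10,000: t = 0.01 / 0.00322 = 3.10, p = 0.002

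The PTAs and the patients are the same throughout; only the simulation size changes.

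**Step 3: MIC levels or MIC-by-pathogen cells as pairs.** Let k of m pairs differ by the same amount d, and let the rest not differ because PTA is near 0 or 1 on both routes. The mean difference is kd/m and the sum of squares about it is kd²(m − k)/m. Hence t = √{k(m − 1)/(m − k)}, and d cancels.

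- One pathogen, k = 2, m = 8: t = √(2 × 7 / 6) = 1.53, 7 df, p = 0.17
- Same pattern for three pathogens, k = 6, m = 24: t = √(6 × 23 / 18) = 2.77, 23 df, p = 0.011

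In this pattern the size of the route difference has no effect on p; the grid decides it.

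**Step 4: rejection rates by simulation.** The following inputs are assumptions, none of them in the documents: log-normal exposure, between-patient log-SD 0.2–0.3, within-patient log-SD 0.1–0.25, true PTA 80–95%, 10 patients. Each route's mean and SD were estimated from the 10 patients and fed to 10,000 draws. MIC grids had 6, 8 or 12 two-fold steps. For the cells, the three pathogens had either the same threshold or thresholds shifted by a third of a two-fold step. There were 18 settings of 2,000 trials each; the per-patient PTA rows used 36 settings of 4,000 trials, with a log-MIC SD of 0.5 or 0.8.

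| Pair | Rejects, no route difference | Rejects, exposure halved on one route |
|---|---|---|
| Simulated draw | 80.6–93.4% | 100% |
| MIC level, one pathogen | 0–0.1% | 0–0.1% |
| MIC-by-pathogen cell | 5.2–54.2% | 54.9–100% |
| Patient, log exposure | 3.8–5.9% | 99.95–100% |
| Patient, own PTA, smooth MIC distribution | 2.5–5.3% | 99.2–100% |
| Patient, own PTA, two-fold MIC steps | 0.3–4.3% | 92.9–100% |

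The near-zero rates for one pathogen's MIC levels belong to two-fold grids and this range of SDs. At half exposure, a between-patient log-SD of 0.5 raised the rate to as much as 18%. In a separate stress case with no route difference (between- and within-patient CV 25% each), MIC grids with half and quarter two-fold steps (13 and 25 levels) rejected in 10% and 58% of trials, against 0% for 7 two-fold levels.

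**The case against.** The strongest reply is that the patient is already the intended pair. The sentence on intra-patient pharmacokinetics and pharmacodynamics stands in the same part of IV.F, the next one refers to 10 patients, PTA is the pharmacodynamic output, and the design is a crossover. On that reading the error rate is at or below about 5%. Much of this stands: patient pairing is the most natural intention. But it does not supply the missing step. PTA has a separate sentence without a unit, and the simulation described yields nothing per patient to enter into the test.

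A reader might infer three stronger things that the documents do not support:

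- *The plan discards patient identity.* It is silent on this. Two figures just before the comparison text are not shown; nothing visible says that they define a pair, but nothing shows that the link to the patient is dropped either.
- *The plan will test 10,000 draws as pairs.* Nothing in IV.F proposes this. That row is a stress case.
- *The finding on adequacy is unsound.* The hypothesis concerns adequacy on each route, judged from concentrations and PTA against targets. A wrong pairing unit would leave the reported PTAs unchanged.

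**Conclusion.** The point holds as a mismatch between the planned test and the described output: the sentence cannot be carried out validly on the simulated PTAs, and the step that would give patient pairs is not written. The arithmetic on draws and cells follows from the t formula and chosen example values. The rejection rates rest on the assumed inputs and show only how much the unit can matter.

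It would go too far to say that only patient pairs keep the error rate at or below 5%. One pathogen's MIC levels on a two-fold grid also stay below it, but because they almost never reject, even at half exposure with between-patient log-SD 0.2–0.3. Of the units examined, patient pairs on log exposure gave close to the nominal rate and also detected a halved exposure.

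The weight is minor to moderate. PTA is not a listed endpoint, the study is described as descriptive, and no stated decision depends on this p-value.

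**What to change.** Replace the PTA sentence in IV.F with:

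> Simulated PTA will be reported descriptively by route, MIC and pathogen. Any IV–IP test will use the 10 patients as pairs (each patient's exposure index, or a PTA computed per patient and route against the MIC distribution); no p-value will be computed across simulated draws, MIC values or pathogens.

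If patient pairs were always intended, this only writes down the unit and the missing step. The cost is wording and a little more computing; no visit, sample or patient is added. Fewer differences may be called significant, and a test on per-patient PTA is conservative when MICs come in two-fold steps (0.3–4.3% in the table above). A test on the exposure index avoids that loss.

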**G. Summarize Knowledge to be Gained:**

This study will determine the pharmacokinetic profile of dalbavancin within the plasma and peritoneal fluid following the administration of dalbavancin intravenously and then intraperitoneally in patients undergoing peritoneal dialysis. This study may also identify possible side effects from intraperitoneal administration of dalbavancin. Determining the pharmacokinetic profile and side effect profile of dalbavancin in patients undergoing peritoneal dialysis may allow for further treatment applications of dalbavancin including peritonitis.

